8.4 Fabry Disease Medical History

Fabry disease medical history by body system and conditions (as collected in the Electronic Case Report Form (eCRF)) will be tabulated by treatment arm and for each of the subgroups in Section 7.4. The analysis will be done on the ITT analysis set.

Information on Fabry disease medical history is collected from 4 different forms within the eCRF: Fabry Disease Medical History, Fabry Disease Diagnosis Per Protocol, Fabry Disease Past Treatment and Mutations Analysis. Data collected on these forms will be listed.

Age of Fabry disease diagnosis will be calculated using intck function in SAS and will be included in the relative listing.

8.5 Other Medical History

Other medical history will be summarized by System Organ Class (SOC) and Preferred Terms (PT) by treatment group and for each of the subgroups in Section 7.4. The analysis will be done on the ITT analysis set. SOC will be sorted alphabetically: within SOC, PT will be sorted in a decreasing order of PRX-102 frequency.

8.6 Treatment Compliance

Treatment compliance will be assessed by the percentage of the number of infusions (partial or complete) out of the expected number of infusions for each patient based on the patient treatment duration. For patients who terminated early, the expected number of infusions will be based on their treatment start date and date of discontinuation. This will be done regardless of reason of discontinuation. Treatment compliance will be summarized by treatment group using the ITT set. For patients whose study was prolonged due to COVID-19, the compliance will be based on their extended time in the study.

Compliance will be summarized also by the following categories: < 60%; $60\% \le$ and < 80%; $\ge 80\%$.

9. ANALYSIS OF PRIMARY EFFICACY ENDPOINT

The primary efficacy endpoint is the mean annualized change (slope) in estimated glomerular filtration rate (eGFR). The eGFR is not measured directly but is derived from the value of the serum creatinine and from patient characteristics, with close to 30 planned visits over 2 years in which the serum creatinine is evaluated.

Four different statistical approaches were considered, in order to compare the annualized slope between the treatment arms. Within the framework of a longitudinal mixed model, two models were considered, a random intercept model (RI) and a random intercept random slope (RIRS) model.

Within the framework of a two-stage approach, the first stage includes estimation of individual slopes using linear regression. Two models were considered for the 2nd stage: Analysis of Covariance (ANCOVA) and quantile regression for comparing the median slopes.

For the interim analysis the models considered were the RIRS, RI and two-stage with ANCOVA. The two-stage with quantile regression was added following a recent publication by Ortiz et al (2021) in which the median eGFR slope of Fabrazyme was compared to the median eGFR slope of un-treated Fabry patients. Unlike linear regression which makes distributional assumptions (i.e., normality), the quantile regression makes no such assumptions, and is robust against outliers (Koenker and Bassett (1978; 1982); Hao and Naiman, D. (2007)).

Following the Ortiz publication, extensive simulations were performed and shared with the FDA, and it was agreed to use the two-stage with quantile regression on the ITT set as the primary model for the final analysis. For non-inferiority, both the ITT and PP should be considered when interpreting the study, so the analysis will be performed also on the PP set.

The two-stage with ANCOVA, RI, RIRS on the ITT and PP will be considered as supportive analyses as they deal with a different estimand.

For all of the analyses discussed in this section, time will be measured relative to day of 1st infusion.

This section is laid out as follows: Section 9.1 discusses the derivation of the eGFR from serum creatinine; Section 9.2 provides technical details for the proposed two-stage with quantile regression model; Section 9.3 describes the planned sensitivity and supportive analysis, Section 9.4 describes the sensitivity analyses to account for missing data, Section 9.5 describes the sensitivity analysis for AKI episodes and Section 9.6 describes the planned sub-groups to be examined for the primary endpoint.

All analysis described in this section will be conducted on the ITT analysis set. In addition, some of the analysis will be conducted also on the PP analysis set as sensitivity analysis

9.1 eGFR Derivation

eGFR will be derived based on the value of the serum creatinine using the CKD-EPI formula and rounded to 2 decimal places:

```
eGFR (mL/min/1.73 m^2) = 141 × min(Scr/\kappa,1)\alpha × max(Scr/\kappa, 1)\alpha × 0.993Age × 1.018 [if female] × 1.159 [if black / African American],
```

where Scr is serum creatinine (mg/dL), κ is 0.7 for females and 0.9 for males, α is -0.329 for females and -0.411 for males, min indicates the minimum of Scr/ κ or 1, and max indicates the maximum of Scr/ κ or 1. Age is the actual age when the patient's serum creatinine is collected.

Results of the serum creatinine test at the screening visit appear twice in the data-base: once as part of the data transferred from the central laboratory and once in the eCRF (once the site receives from the central laboratory, the value is entered into the eCRF to check the eligibility in terms of eGFR value and the eGFR slope). These two values should be identical. In the listings, by-visit tables of eGFR and slope calculations, the value entered into eCRF should be used anyway.

In case of two identical serum creatinine measurements taken at same date and time but assigned to two different visits, then it should be used only once and assigned to the visit that was performed on that date.

AKI Episodes are reported by the investigators as an AE. Serum creatinine measurements, if any, during an AKI episode will be excluded from the eGFR summary tables and any analysis related to eGFR. An AKI episode is defined between the start and the end date of the AKI AE. The number of eGFR measurements which are excluded from the analysis will be summarized by treatment arm.

eGFR values associated with the AKI events will only be listed (and flagged to identify that they were excluded from tables).

The eGFR values and the change from Baseline in these values will be summarized by visit and treatment arm for the ITT and the PP set.

In case that serum creatinine value (and hence eGFR) is missing in a planned visit, but the test was performed up to 17 days after the date of the planned visit, the serum creatinine and eGFR will be mapped to the planned visit and will be included in the summary tables by visit.

Mean eGFR values and change from baseline over time will be plotted by treatment group as well as a graph of eGFR boxplots over time.

9.2 Primary Efficacy Analysis – Two Stage with Quantile Regression

This analysis will be performed on the ITT and the PP analysis sets.

With this approach, at the first stage, the individual annualized mean change (slope) in eGFR will be estimated for each patient using the following linear regression model:

eGFR =
$$\alpha + \beta \times$$
 [time in year].

The slope β (mL/min/1.73 m² / year) will be an estimate of the individual patient's annualized mean change in eGFR. The "[time in year]" in the formula denotes time measured in years, from Baseline (defined for the purpose of the calculation as date of 1st infusion) to the respective visit, and will be estimated by (date of the visit – date of Baseline)/365.25. All data points for a patient will be used to estimate the slope, excluding any eGFR values measured during an AKI episode, which will be considered missing. For patients whose study was prolonged in light of COVID-19, the additional eGFR measurements will be included in the analysis. The linear model will be fit for all patients with at least 4 eGFR measurements (after exclusion of eGFR during AKI). For patients with fewer than 4 measurements, the slope will be missing. Considering the low rate of early termination and high compliance with visits, it is expected that the number of patients with missing slopes will be very low. The individual slopes obtained at the 1st stage of the analysis will be summarized descriptively and individual slopes will be listed.

At the 2nd stage, the annualized mean change (slope) of the eGFR between the two treatment arms will be compared using quantile regression estimating the median slopes. The dependent variable will be the slope of each individual patient and the model will include the following covariates:

- Intercept
- Treatment arm (PRX-102; agalsidase beta). This is the main parameter of interest.

The estimated median slopes for the two treatment groups and their difference, and the corresponding 95% CI obtained from the quantile regression will be presented. The quantile regression analysis will be implemented using SAS PROC QUANTREG with the code and detailed description provided in Appendix A.2 (Section 17).

Non-inferiority will be declared if the lower bound of the confidence interval for the treatment difference (PRX-102 minus agalsidase beta) is greater or equal to -3.0 mL/min/1.73 m²/year.

9.3 Sensitivity and Supportive Analyses for the Primary Analysis

Several sensitivity and supportive analyses will be conducted. The sensitivity analysis will deal with the same estimand as the primary analysis, and will differ in the covariates used. The supportive analysis will deal with a different estimands (mean using RIRS, RI, and two-stage with ANCOVA; mean eGFR change from baseline using a Mixed Model Repeated Measure (MMRM) and other quantiles using quantile regression. Additional sensitivity analysis may be conducted as post-hoc. In such case, they will be reported as post-hoc in the CSR.

A forest plot will be created that includes the results of the primary analysis as well as sensitivity and supportive analyses described in this section and in Section 9.4.

All the analyses described in this section will be conducted on the ITT and PP sets.

9.3.1 Sensitivity Analysis – Two Stage with Quantile Regression – Different Covariates

The two-stage with quantile regression will be repeated, where in addition to the intercept and treatment arm, the model will include the stratification factor ((UPCR ≤ 1 ; ≥ 1 gr/gr).

The estimated median slopes for the two treatment groups and their difference, and the corresponding 95% CI obtained from the quantile regression will be presented. The estimated median for the two groups will be done for the balanced case as described in Appendix A.2 (Section 17).

Non-inferiority will be declared if the lower bound of the confidence interval for the treatment difference (PRX-102 minus agalsidase beta) is greater or equal to -3.0 mL/min/1.73 m²/year.

9.3.2 Supportive Analysis – Random Intercept Random Slope Longitudinal Model

The analysis compares the annualized mean change (slope) of the estimated glomerular filtration rate (eGFR) between the PRX-102 group and the agalsidase beta (Control) group. A random intercept random slope longitudinal mixed model will be used to compare the eGFR slopes of the two groups.

The general form of the mixed model is,

$$Y = X\beta + Zb + \varepsilon$$

where Y denotes the eGFR values at the different time points. The design matrix, X, represents the fixed part of the model and will include the following terms:

- Intercept
- Treatment arm (PRX-102; agalsidase beta)
- Time (actual time of measurements (in years) considered as a continuous variable)

• Treatment arm by time interaction. This is the main parameter of interest.

The random effect part, Z, will include a random intercept and a random slope and an unstructured covariance matrix (dimension 2 X 2) will be used. The covariance of the error term, ε , is assumed to be a diagonal matrix with equal variances along the diagonal. The restricted maximum likelihood approach will be used to estimate the variance components, and the Kenward-Roger approximation will be used to estimate the denominator degrees of freedom.

For patients whose study was prolonged in light of COVID-19, the additional eGFR measurements will be included in the analysis. All eGFR values collected during an AKI episode will be set to missing. Missing data (due to AKI or other reasons) will not be imputed.

The estimated slopes for each of the two treatment groups will be obtained from the mixed model and the estimated difference in slopes is the coefficient associated with the time by treatment interaction term. The corresponding 95% confidence intervals (CI) for all three estimates will be presented. The analysis will be implemented using SAS PROC MIXED with the code and detailed description provided in Appendix A.2 (Section 17).

Non-inferiority will be declared if the lower bound of the 95% CI for the interaction term of treatment group by time is greater or equal to -3.0 mL/min/1.73 m²/year, the prespecified non-inferiority margin.

9.3.3 Supportive Analysis: Two-Stage Approach Using Analysis of Covariance

The 1st stage of this approach is identical to the 1st stage of the two-stage with quantile regression.

At the next stage, the annualized mean change (slope) of the eGFR between the two treatment arms will be compared using Analysis of Covariance (ANCOVA). The dependent variable will be the slope of each individual patient and the model will include the following covariates:

- Intercept
- Treatment arm (PRX-102; agalsidase beta). This is the main parameter of interest.

The estimated means of the slopes for the two treatment groups and their difference, and the corresponding 95% CI obtained from the ANCOVA model will be presented. The ANCOVA analysis will be implemented using SAS PROC MIXED with the code and detailed description provided in Appendix A.2 (Section 17).

Non-inferiority will be declared if the lower bound of the confidence interval for the treatment difference (PRX-102 minus agalsidase beta) is greater or equal to -3.0 mL/min/1.73 m²/year.

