3.1 Sample Size and Statistical Power Consideration

The section below is based on the plan at the time of the protocol and does not reflect the change in the planned analysis for the final analysis. The number of patients randomized was 78, as planned.

This orphan indication allows for a small number of patients, given the rarity of the disease and the difficulties in allocating patients for clinical trials. Two tests are planned to be performed as part of the primary efficacy analysis for this protocol. The first test, to test the non-inferiority hypothesis, will be performed using data collected after the last patient have at least 12 months of treatment (interim analysis). The second test, to test the superiority hypothesis, will occur with the data from 24 months of treatment (final analysis). We now describe the statistical power/sample size considerations for these two tests.

Sample Size and Power for the Non-Inferiority Analysis (Interim Analysis)

With a total of approximately 66 patients in 2:1 randomization ratio there is at least 90% power to demonstrate the non-inferiority of PRX-102 vs. agalsidase beta in terms of mean annualized change (slope) in eGFR. The power is computed assuming one-sided two-sample t-test with a one-sided alpha level of 0.025 and the non-inferiority margin of -3.0 mL/min/1.73 m²/year. The true difference in slopes is assumed to be 1.1 mL/min/1.73 m²/year in favor of PRX-102 and the standard deviation of the slopes being 1.5 mL/min/1.73 m²/year in each group.

Sample Size and Power for the Superiority Analysis (Final Analysis)

With a total of approximately 66 patients in 2:1 randomization ratio there is approximately 80% power to detect a difference of 1.1 mL/min/1.73 m²/year between the mean annualized change (slope) in the two arms. The power is computed assuming two-sample t-test at two-sided alpha level of 0.05 and the standard deviation of the slopes being 1.5 mL/min/1.73 m²/year in each group.

For this analysis the null hypothesis is that the difference in mean annualized change in eGFR between the treatment groups is 0 versus an alternative hypothesis that it is not 0.

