17. APPENDIX A.2 – PRIMARY, SECONDARY, SENSITIVITY AND SUPPORTIVE ANALYSES SPECIFICATIONS

17.1 Random Intercept Random Slope Specifications

The pseudo code presented in this section relates to the analysis described in Section 9.3.29.2, and may need adjustment at the time of analysis. This code to be used in the CSR will be finalized within the programming specifications.

The dependent variable, Y, is eGFR values at different time points (from the baseline visit and onwards, including unscheduled visits). The fixed part of the model includes the following terms: treatment arm (denoted by TRT with 1st level for PRX-102 and 2nd level for AGALSIDASE BETA), time (actual time of measurements in years; denoted by TIMEYR), and treatment arm by time interaction (denoted by TIMEYR*TRT).

```
proc mixed data = DATA1 method=reml alpha=0.05 covtest;
class SUBJID TRT;
model eGFR = TRT TIMEYR TRT * TIMEYR / s ddfm = KR cl;
random INTERCEPT TIMEYR / subject=SUBJID type = UN;
estimate "PRX-102" INTERCEPT 0 TRT 0 TIMEYR 1 TRT*TIMEYR 1 0
/ cl;
estimate "ADALSIDASE BETA" INTERCEPT 0 TRT 0 TIMEYR 1 TRT*TIMEYR 0 1
/ cl;
estimate "EFFECT" INTERCEPT 0 TRT 0 TIMEYR 0 TRT*TIMEYR 1 -1
/ cl;
run;
```

SUBJID denotes the patient ID, DATA1 represent the data to be used for the analysis. Non-inferiority will be assessed based on the lower bound of the confidence interval obtained from the estimate statement labelled as "EFFECT".

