17.4 Two-Stage Analysis – Stage 2 Specification

In the 2nd stage of the two-stage approach, a ANCOVA model will be fitted. The pseudo code presented in this section relates to the analysis described in Section 9.3.3 9.3.3 and may need adjustment at the time of analysis.

The dependent variable, Y, will be the slope for each patient which was estimated using simple regression. The covariate is treatment arm (denoted by TRT).

```
proc mixed data = SLOPES1 method=reml alpha=0.05 covtest;
class SUBJID TRT;
model SLOPE = TRT / s ddfm = KR cl;
lsmeans TRT/diff cl;
run;
```

SLOPES1 denotes the slopes of each patient.

Non-inferiority is assessed based on the lower bound of the confidence interval obtained from the LSMEANS statement.

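### Two of the three supportive mean-slope analyses (two-stage ANCOVA and RIRS) assume one slope variance for both arms under 2:1 allocation, so their intervals are too narrow if the smaller control arm varies more

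*SAP*

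**What the plan says.** For the two-stage approach, SAP section 9.3.3 states that "the annualized mean change (slope) of the eGFR between the two treatment arms will be compared using Analysis of Covariance (ANCOVA". The code in section 17.4 is "model SLOPE = TRT / s ddfm = KR cl", with no statement that lets the residual variance differ by arm.

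For RIRS, section 9.3.2 says of the random effects that "an unstructured covariance matrix (dimension 2 X 2) will be used", and takes the error variance as constant. The code in section 17.1 is "random INTERCEPT TIMEYR / subject=SUBJID type = UN", again with no grouping by arm.

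The third mean-slope analysis, the random-intercept model (sections 9.3.4 and 17.2), uses the EMPIRICAL sandwich estimator.

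Allocation is 2:1, planned as about 52 and 26 patients (SAP sections 3.1 and 3.2). The only information on spread is a planning assumption, the "standard deviation of the slopes being 1.5 mL/min/1.73 m²/year in each group". All three mean-slope models are labelled supportive at the final analysis (section 9). Even so, sections 9.3.2 and 9.3.3 each give a rule for declaring non-inferiority when the lower bound is at or above -3.0 mL/min/1.73 m²/year.

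**The concern.** A pooled variance weights each arm by its degrees of freedom: at 52 and 26 patients, 51 of 76 come from PRX-102 and 25 from control. The variance of the difference weights the arms the other way. With equal SDs, the controls already contribute (1/26)/(1/52 + 1/26) = two thirds of it. If the arms differ in spread, the pooled standard error is therefore wrong, and the direction depends on which arm is the more variable.

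Equal spread is an assumption here, since one arm switches enzyme and the other continues. Kenward-Roger in section 17.4 cannot repair this, because the model contains only one variance to adjust. At stake is whether two intervals offered in support of the primary result, on both ITT and PP, hold their nominal level.

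**Working it through.** **Inputs.** SAP section 3.1 gives the test "with a one-sided alpha level of 0.025 and the non-inferiority margin of -3.0" mL/min/1.73 m²/year, an SD of 1.5 in each arm, 52/26 randomized and 44/22 completers. It also says: "The true difference in slopes is assumed to be 1.1 mL/min/1.73 m²/year in favor of PRX-102". Unequal SDs are not in the documents. The control/PRX-102 SD ratios of 0.5 to 3 used below are assumptions.

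**The plan's own figure.** Section 3.1 says "there is approximately 80% power to detect a difference of 1.1 mL/min/1.73 m²/year" with about 66 patients.
- SE = 1.5 × √(1/44 + 1/22) = 0.392, and 1.1/0.392 = 2.81.
- Normal approximation: Φ(2.81 − 1.96) = 80.2%. Noncentral t with 64 df: 79.0%. The figure reproduces.
- The stated non-inferiority power of at least 90% also holds: the distance to the margin is 1.1 + 3.0 = 4.1, and power exceeds 99.9%.

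**Pooled against true standard error, 52/26, PRX-102 SD 1.5, control SD 2.25 (ratio 1.5).**
- True variance = 2.25/52 + 5.0625/26 = 0.0433 + 0.1947 = 0.2380; SE 0.488.
- Pooled variance = [(51 × 2.25 + 25 × 5.0625)/76] × (1/52 + 1/26) = 3.175 × 0.0577 = 0.1832; SE 0.428.
- Ratio = 0.428/0.488 = 0.88.

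**Opposite direction, PRX-102 SD 2.25, control SD 1.5.**
- True variance = 5.0625/52 + 2.25/26 = 0.1839; SE 0.429.
- Pooled variance = [(51 × 5.0625 + 25 × 2.25)/76] × 0.0577 = 0.2387; SE 0.489.
- Ratio = 1.14, so the interval is about 14% too wide.

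**Simulation.** 400,000 trials per setting, 52/26, true difference at -3.0, pooled t interval as coded:

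| Control/PRX-102 SD | Pooled SE / true SE | Coverage of 95% CI | One-sided error |
|---|---|---|---|
| 0.5 | 1.23 | 98.3% | 0.8% |
| 0.67 | 1.14 | 97.4% | 1.3% |
| 1 | 1.00 | 95.0% | 2.5% |
| 1.25 | 0.93 | 93.2% | 3.4% |
| 1.5 | 0.88 | 91.5% | 4.3% |
| 2 | 0.81 | 88.9% | 5.5% |
| 3 | 0.76 | 85.9% | 7.0% |

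Error and coverage at 44/22 agree to about 0.001. With separate variances and Satterthwaite degrees of freedom, the one-sided error is 2.5% to 2.6% in every row. The cost when the SDs are equal is 0.7% in interval width.

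**Does this carry over to RIRS?** In six simulated data sets with 30 balanced visits, the RIRS standard error of the slope difference equalled the pooled two-stage one to four decimals. With incomplete follow-up the correspondence is approximate.

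**Random-intercept model.** In the same six data sets its sandwich standard error equalled the arm-specific one (uncorrected form). With a normal quantile, that form has a one-sided error of 3.0% at ratio 1 and 3.3% at ratio 3. This is nearly flat in the SD ratio; the small excess comes from the missing small-sample correction, not from pooling.

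**Effect on conclusions at a true difference of 0.** At ratio 2, the pooled and separate-variance intervals conclude non-inferiority in 99.9% and 99.6% of trials (52/26), or 99.7% and 98.9% (44/22). They separate at ratio 3: 96% against 89% at 52/26.

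**The case against.** The strongest reply is that little depends on these two models. The primary analysis is quantile regression of the median with a resampling interval. Section 7.6.2 says that supportive analyses carry no claims of significance. The plan already includes one variance-robust mean-slope analysis, the random-intercept model, which appears in the same forest plot. Stage-one slopes are also summarized descriptively, and the 25th and 75th percentiles are compared, so unequal spread would be visible. All of this stands and limits the point to an optional improvement. It does not remove it, because sections 9.3.2 and 9.3.3 still give declaration rules based on these intervals.

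A second reply concerns direction. If switching enzyme changes the spread, it could as easily add variance to the switching arm, where pooling is conservative. This stands too. A reader might infer that the control arm is the more variable one and that non-inferiority is therefore declared too easily. The documents give no arm-specific SD and do not support that. Nor does pooling always do harm when allocation and variances are both unequal: at ratios below 1 the error is below 2.5%.

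A reader might also infer that the interim result was affected, since RIRS was the primary model then (section 13.2). Without SDs by arm this cannot be judged, and the present SAP governs only the final analysis.

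Finally, the RIRS change is not free: it doubles the covariance parameters from four to eight, with only about 26 controls.

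**Conclusion.** The point holds for the two-stage ANCOVA and RIRS only, and it is conditional. For assumed control/PRX-102 SD ratios of 1.25 to 2, one-sided error at the margin rises from 2.5% to between about 3.4% and 5.5%. If PRX-102 is the more variable arm, the loss is precision instead. These figures assume normally distributed slopes, the planned 52/26 split, a true difference exactly at -3.0 and, for RIRS, balanced follow-up.

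Two stronger readings do not hold. It is not true of all the mean-slope analyses, because the random-intercept model is protected. It also does not put the final non-inferiority decision in doubt, because that rests on the quantile regression. This is a low-cost improvement to two supportive analyses.

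**What to change.** - **Two-stage ANCOVA.** In section 17.4 add `repeated / group=TRT;` and keep `ddfm=KR`. State in section 9.3.3 that the slope variance is estimated separately by arm. Cost: one code line, one sentence, and about 1% in interval width if the variances are in fact equal.
- **RIRS.** In section 17.1 add `group=TRT` to the RANDOM statement and `repeated / group=TRT;` for the residual. State this in section 9.3.2, with the common-variance fit as the pre-stated fallback if the model does not converge. Cost: four further covariance parameters and some risk of non-convergence.
- **Reporting.** Show the slope SD by arm beside both analyses, so that a reader can see whether the variance assumption mattered.

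The change should be fixed before the final database lock, so that the variance structure is not chosen after the results are seen.
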